4.2 Study Outcome Measures

4.2.1 Primary Outcome Measures

The primary outcome of this trial is ACP documentation any time during the index hospitalization as ascertained by NLP-assisted EHR review for any qualifying documentation of ACP in the EHR note (goals of care, advance directive, MOLST/POLST, code status, palliative care or hospice) (yes versus no).

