4.2.2 Secondary Outcome Measures

Secondary outcomes include:

- Code status preferences (Aim 1)
- Use of palliative care consult/services (Aim 1)
- Hospice use (Aim 1)
- Health Care Proxy (Aim 1)

Secondary outcomes related to Aim 2a (patients 18+ years admitted to one of the study inpatient units with ADRD/delirium) include:

- Documentation of ACP Preferences in Electronic Health Record

Secondary outcomes related to Aim 2b (caregivers of patients with ADRD/Delirium) include:

- ACP knowledge (Aim 2)
- Confidence in future care (Aim 2)
- Communication satisfaction (Aim 2)
- Decisional satisfaction (Aim 2)
- Decisional conflict (Aim 2)

5 Study Design

This is pragmatic SW-CRT of a PCE-led, video-assisted COVID-19 ACP intervention in inpatient-based units (3 medical-surgical wards, Medical ICU, Cardiac ICU, Neurology ICU, step-down unit) at two hospitals: BMC and North Shore University Hospital (Northwell Health). All inpatients ≥ 65 and all patients with ADRD/Delirium ≥ 18 who are hospitalized on a unit during the intervention phase will receive the intervention.

This 2-year study (2 month data collection and tool preparation, staff training and site standardization (we are already embedded in both health systems doing similar work; thus this

short timeframe is feasible); 16 months rolling recruitment and surveying; 2 months data cleaning and analysis, and 4 months manuscript preparation and dissemination of findings) will roll out the intervention to 14 randomized inpatient units at 2 sites. Every two months, an additional inpatient unit will be added to our intervention at each hospital, i.e., there will be seven waves or "steps"; for a total of 7 units at each hospital.

Consistent with a SW-CRT with two hospital units per step (cluster), prior to the collection of any data in the pre-intervention period, we will generate a set of uniform random numbers for each of the seven clusters to be assigned to a starting period for the study intervention. There will be eight study periods in total with a usual care period at the start of the study for all clusters. The first randomized intervention period will then begin in period two.

Cluster	Baseline	14 Months of Clustered Intervention Expansion							
	M0	M2	M4	M6	M8	M10	M12	M14	
1									
2									
3									
4									
5									
6									
7									

The data needed to assess the outcomes for all patients will be derived from each hospital's EHR (Aim 1).

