For Aim 1, there are special informed consent considerations in this pragmatic SW-CRT: the hospital clinical unit is the level of randomization, the intervention is of low risk and will be implemented as the standard of care for the whole clinical unit, and data for our primary outcome and related outcomes derived from the EHR are ascertained from existing sources. Thus for this aspect of our proposal, we will seek a waiver of individual informed consent and HIPAA authorization after careful review of the criteria to do so as we have previously done successfully in prior studies. The research involves no more than minimal risk to the subjects as described above. We do not believe the waiver will adversely affect the rights and welfare of the subjects. As a pragmatic trial of thousands of hospitalized patients and clinicians, this research could not practicably be carried out without the waiver nor without access to and use of PHI of patients.

For Aim 2a, we will seek a waiver of individual informed consent and HIPAA authorization due to the fact that this is a low risk activity (chart review), and the target population is incapable of consent due to a diagnosis of ADRD/Delirium.

For Aim 2b, verbal informed consent will be obtained for the phone survey. The caregiver survey should take less than fifteen minutes.

Natural Language Processing (NLP) Data Collection

Over the course of the study, we will review the charts for all enrolled participants. For Aim 1 and Aim 2a, the inpatient EHR records (including those with ADRD/Delirium) will be analyzed (approximately 15,000 patients across both sites).

Initial NLP analyses will be done locally at each data collection site (BMC and Northwell) using software that was developed at DFCI for this purpose. The results of that initial analysis will be coded and sent as a HIPAA LDS via HIPAA approved cloud folders such as Box.com to our NLP partners at DFCI. Each site will retain a local mastercode file that will not be shared with anyone outside the institution. Patients will be assigned a unique identifier that will be used on datasets shared with DFCI.

DFCI will have a reliance agreement in place with BUMC and Data Transfer Agreements in place with both BMC and Northwell.

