12.3 Statistical Methods

Statistical Analysis: For the primary analyses of the primary and secondary outcomes, there will be no crossover of data for subjects from usual care to the intervention during the study; that is, subjects will only contribute data once during the course of the study, from their index hospitalization. Similarly, patients who move units during the course of their index hospitalization will be assigned to contribute intervention time data if they spend at least eight daytime weekday hours after being identified as meeting the inclusion criterion on a clinical unit where the intervention is being conducted. Accordingly, data being contributed by patients at each site during the pre-intervention period and data being contributed by patients after the initiation of the intervention will be kept separate for initial analyses. However, because we expect some patients to have multiple hospitalizations during different steps or to different units (i.e., crossover design), we will perform secondary analyses on all outcomes including data from the index hospitalization. This will include stratified sensitivity analyses of patients who contribute data (a) only to control period; (b) only to intervention period; or, (c) to both control and intervention periods.

Given the randomized nature of the stepped wedge design, we will report our results according to CONSORT guidelines. For the aims of the study that require patient/caregiver enrollment (Aim 2), we will record the number of people approached, screened, ineligible, and refusing participation. We will record subject attrition and note all adverse events. We will employ the intent-to-treat principle in our comparative analyses between the intervention and usual care groups. All hypothesis tests will employ a two-sided alpha level of 0.05. Given that the primary aim will be addressed by the analysis of data obtained from available patient records for the study period, we will examine the distributions of relevant variables focusing on the data relating to the documentation of ACP, the outcome of this aim. For the secondary aims of the study that will require enrollment of a caregiver sample for interview (Aim 2), we will examine the

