distributions of the uncertainty and knowledge scale scores, the outcomes of interest between intervention and usual care subjects, as well as the distributional characteristics of all other salient study variables. We will generate descriptive statistics (means, standard deviations, quantiles for continuous variables; counts and percentages for categorical variables) and schematic plots (box-and-whisker, quantile-quantile plots). Given the nature of the cluster randomization that we will employ, we will utilize statistical analytic methods that take the correlated nature of the data into account as well as the influence of time to account for secular trends. In this study, we will examine both the health system and hospital unit as clustering variables, with the hospital unit as the primary clustering variable. We will compare the intervention and usual care groups on salient variables in order to assess balance in the distributions of these variables. Variables found to differ between the study groups will be further evaluated to assess their confounding effects of intervention vs. usual care differences on outcomes in multivariable analyses for correlated (clustered) data.

Aim 1. To test the combined effects of a COVID-19 ACP Educator-led, video-assisted palliative care intervention on rates of: ACP documentation; Medical orders for resuscitation preferences in the EHR; Palliative Care Consults; and, Hospice use. ***Hypothesis: A higher proportion of patients in the intervention phase (vs. control) will: complete ACP documentation (primary trial outcome), have documented orders for resuscitation preferences, have palliative care consults, and enroll in hospice.***

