Primary outcome: ACP documentation. In order to formally estimate and test differences in the proportion of patients with documentation of ACP between the intervention and usual care groups, we will employ logistic regression models for correlated binary outcome data. These models will either involve the use of robust variance methods to account for the clustering of these data by hospital site and/or health system via generalized estimating equations (GEE) or the inclusion of a random effects terms (in which case, the results will be interpreted as cluster-specific). Other potential modifiers of the effect of intervention, confounding variables, or covariates can be added to this model as fixed effects. Although we do not expect effect modification in the study data, we will examine the potential for such effects (interaction) through the use of stratified analyses and the inclusion of interaction terms with study group in our statistical models. Candidate effect modifiers will be specified a priori and will include age, gender, race/ethnicity, religion, and language. We will also examine and incorporate secular trend effects, i.e., the effect of time over the course of the study. Statistically significant interactions with the intervention will be retained and the nature of heterogeneous intervention effects will be estimated using the interaction model.

Based on our prior work in which we exhibited the fact that African-American and Hispanic patients are at particularly high risk for lower level of knowledge related to ACP, not discussing ACP with family, not having a health care proxy, and not having ACP documentation, we anticipate that this intervention may be particularly beneficial for African-American and Hispanic patients.(115, 131, 132) Accordingly, we will evaluate heterogeneous treatment effects by race and ethnicity and anticipate having adequate diversity in our study population to make such assessments. All data regarding Aim 1 will come from the EHR. Our institutions maintain excellent self-report information regarding race and ethnicity.

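### For patients who change units, the primary analysis sets the arm by hours on an intervention unit after admission. This departs from assignment by randomised unit and leaves some movers' arm, and the cluster of unit-to-unit movers, unstated.

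*Combined protocol and SAP*

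**What the plan says.** All references are to the combined protocol and SAP.

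- **Arm of movers.** Section 12.3, writing about the primary analyses, says that patients who change units during the index stay are "assigned to contribute intervention time data if they spend at least eight daytime weekday hours after being identified as meeting the inclusion criterion" on a unit where the intervention is running. No minimum stay applies to patients who remain on one unit.
- **Analysis principle.** The same section states: "We will employ the intent-to-treat principle in our comparative analyses between the intervention and usual care groups".
- **Level of randomisation.** Section 9 (Informed Consent) says that "the hospital clinical unit is the level of randomization".
- **Outcome window.** Section 4.2.1 defines the primary outcome as "ACP documentation any time during the index hospitalization".
- **Setting.** Section 5 places the trial in "inpatient-based units (3 medical-surgical wards, Medical ICU, Cardiac ICU, Neurology ICU, step-down unit) at two hospitals". Each hospital adds one unit per step, so its seven units all start at different times.
- **Clustering.** Section 12.3 will examine health system and unit, "with the hospital unit as the primary clustering variable". For the primary outcome, "we will employ logistic regression models for correlated binary outcome data", with clustering there described by site, by health system, or both.
- **Adjustment.** "Variables found to differ between the study groups will be further evaluated to assess their confounding effects", using a 10% change-in-estimate screen. Length of stay is not named.
- **Extra units.** Section 7.1 adds nine units, outside the wedge, that supply control participants only.

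**The concern.** In a unit-randomised trial, intent-to-treat normally means analysing patients in the arm of the unit that brought them into the study. Here a patient who enters on a control-phase unit and later transfers becomes an intervention patient once eight qualifying hours have accrued. Whether that happens depends on the transfer, the length of stay and the day of the week, all of which come after entry.

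Longer stays make eight hours more likely within every calendar period, so adjusting for secular trend does not remove the imbalance. A longer stay also leaves more time for any note to be written. Because the outcome covers the whole stay, a note written on a control unit before transfer can be credited to the intervention.

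Two points are also left open. The rule says what happens if eight hours are reached. It does not say what happens to a mover who starts on an intervention unit and leaves sooner. And no rule says which unit is the cluster for a patient who moves between two study units. Two analysts following the text faithfully could build different primary datasets.

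**Working it through.** **Text check.** Each hospital's seven wedge units start at seven different steps, so any move between two of them changes both unit and step. The unit is the primary clustering variable, so the mover's cluster has to be stated, and it is not. The alternative wording for the primary model (site or health system) does not say which level governs. A patient who moves between a study unit and a non-study unit has only one study unit, so that cluster is not in doubt.

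**No plan figure to reproduce.** The documents give no mover share, stay distribution or link between stay and documentation. Everything below on size is illustrative.

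**Simple null calculation.** Assume 20% movers, half of whom reach eight hours; documentation of 25% in non-movers, 30% in movers reaching eight hours and 20% in other movers; the remaining movers count as control; no true effect.

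- Intervention: (0.40 × 0.25 + 0.10 × 0.30) / 0.50 = 0.13 / 0.50 = 26%.
- Control: (0.40 × 0.25 + 0.10 × 0.20) / 0.50 = 0.12 / 0.50 = 24%.
- Spurious difference: 2.0 points. It is 1.0 at 10% movers and 3.0 at 30%.

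**Simulation of the stepped wedge.** From the documents: 14 units (seven per hospital), seven steps, eight periods. Assumed: moves within hospital and within the wedge; daytime weekday is Monday to Friday, 08 to 17; admission uniform over the week; stay lognormal with median 4 days and log-SD 0.8; one transfer at 10 to 90% of the stay. Rising link: documentation hazard 6% per day. Short-stay link: 55% documented under 2 days, 20% otherwise. The model is linear with period and unit effects.

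Null bias in percentage points:

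| Reading of the rule | Stay link | 10% movers | 20% | 30% |
|---|---|---|---|---|
| One-way, cluster = first unit | rising | +0.6 | +1.3 | +1.8 |
| One-way, cluster = unit where the hours accrued | rising | +0.4 | +0.8 | +1.1 |
| One-way, cluster = first unit | short-stay | -0.5 | -1.0 | -1.4 |
| Two-way, cluster = first unit | rising | +1.8 | +3.3 | +4.5 |
| Two-way, cluster = first unit | short-stay | -1.6 | -3.0 | -4.1 |
| Either reading | unrelated | 0 | 0 | 0 |

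One-way means that intervention-first movers stay intervention; two-way means that movers below eight hours become control. The cluster convention barely changes the two-way figures. At 5% movers the bias is about 0.35 points either way (one-way) or 0.9 to 1.0 (two-way) with first-unit clusters. First-unit assignment stays near zero throughout.

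At 20% movers the arm differs from first-unit assignment in 2.3% (one-way) or 3.9% (two-way) of all patients. The unstated arm concerns about 16% of intervention-first movers. In the rising case, about 52% of the documentation in movers switched to intervention predates the transfer.

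**Scale.** Standard error by the Hussey-Hughes formula:

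Var = Iσ²(σ² + Tτ²) / [(IU − W)σ² + (U² + ITU − TW − IV)τ²]

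- I = 14, T = 8, U = 56, W = 560, V = 280. So IU − W = 224 and U² + ITU − TW − IV = 3136 + 6272 − 4480 − 3920 = 1008.
- At 30% documentation the variance is 0.21. With ICC 0.01 (section 12.2), τ² = 0.0021. With 15,000 records over 112 unit-periods (133.9 each), σ² = 0.2079 / 133.9 = 0.00155.
- Var = 14 × 0.00155 × (0.00155 + 0.0168) / (224 × 0.00155 + 1008 × 0.0021) = 0.000162, so SE = 1.27 points. With 9,000 records it is 1.61.

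At 5% movers the bias is therefore below one standard error. At 30% movers, with the full rising link and the two-way reading, it is 4.5 / 1.27 = 3.5 standard errors.

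**With a true effect.** Suppose patients with at least eight hours of exposure gain 10 points and 20% move (first-unit clusters). The eight-hour estimate runs from 8.1 to 10.4 (one-way) or 6.4 to 12.7 (two-way), depending only on the assumed stay link. First-unit assignment gives 8.1.

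**The case against.** Patients are not themselves randomised, and any unit-randomised trial with transfers needs an attribution rule. This one is prespecified, applies only to movers, and does not ask whether the educator was seen. The documents never define intent-to-treat as assignment by unit; that follows from the level of randomisation, which is stated in a consent paragraph. All this stands. A reader might infer that the plan uses an as-treated analysis. It does not: the rule turns on opportunity, not receipt.

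First-unit assignment misattributes too, because documentation prompted by the educator after a transfer would count as control. With no stay link it gives 8.1 points at 20% movers against 9.1 for the one-way eight-hour rule. Its stability across stay links also assumes that the true effect is the same whatever the stay. The choice is therefore partly one of estimand, but the plan does not present it as one.

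The planned confounder screen offers partial protection. Adding five stay categories cuts the simulated null bias to 0.3 points or less. But stay is not named and is itself measured after assignment. With a 10-point exposed effect in the logistic model (one-way, rising link), adding stay changes the log odds ratio by about +7, +1 and -4% at 10, 20 and 30% movers, so a 10% screen would leave it out. The planned strata (control only, intervention only, both) are secondary and formed after admission.

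**Conclusion.** The point holds and should be fixed. It rests on the text: in the primary analysis a mover's arm depends on events after admission, in tension with the stated intent-to-treat principle. The arm of intervention-first movers below eight hours is not stated, nor is the cluster of patients who move between two study units.

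Over 5 to 30% movers and both cluster conventions, the illustrative null bias is:

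- one-way: roughly 0 to +1.8 points if documentation rises with stay, -0.2 to -1.4 if short stays are highly documented;
- two-way: roughly +0.7 to +4.5, or -0.7 to -4.1;
- zero if stay and documentation are unrelated.

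None of these reaches the 10-point benchmark in section 12.2, and all rest on assumed mover shares, stays and stay links.

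Three stronger readings are not supported. A reader might infer that the rule inflates the effect, but the sign is unknown. A reader might infer that every mover lacks a cluster, but only moves between two study units raise that question. A reader might take movers below eight hours to be control; that is a natural inference, but it is not written, and the two-way figures depend on it.

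**What to change.** In section 12.3:

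1. For the primary analysis, assign arm and cluster by the study unit where the patient first meets the inclusion criterion in the index hospitalization, and by that unit's phase on that date, whatever transfers follow. Say whether the nine control-only units in section 7.1 count as study units for this purpose.
2. Keep the eight-hour rule as an exposure-based sensitivity analysis. State the arm of movers below eight hours and the cluster of patients who move between study units.
3. Report the share of patients who move, and the share of movers whose arm differs between the two rules.
4. State whether the 10-point benchmark in section 12.2 refers to the effect of assignment or of exposure.

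The work is SAP wording and one EHR field (first qualifying unit, with date). The real cost is dilution. Under the assumptions above, a 10-point effect in exposed patients is estimated at 8.6, 8.1 and 7.6 points with 10, 20 and 30% movers, against 9.2 with no movers, so item 4 matters. Power remains at least 99.5% at ICC 0.01, even with 9,000 records: at 30% movers, 7.6 / 1.61 = 4.7 standard errors.

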12.2 Sample Size Determination

Statistical power and sample size: All sample size estimates here assume a minimum of 80% power and a two-sided alpha of 0.05. We employ the method for the computation of sample size for cross-sectional stepped wedge studies comparing intervention to usual care in two-group statistical analyses. This method incorporates information on the number of steps used in the

stepped wedge/cluster randomized design, the number of subjects per time period, and the degree of clustering via the intraclass correlation coefficient (ICC) to compute the design effect, the factor by which the sample size found to provide sufficient statistical power for a meaningful intervention difference in outcome assuming independent data is multiplied. For the primary outcome of the documentation of ACP in the medical record, a sample size of 440 records per group in a chi-squared test for independent data will provide 80% power at a two-sided alpha of 0.05 to detect a difference in the proportion of subjects with notation of 35% in the intervention group compared to 25% in the usual care group, values consistent with prior research and expectation based on clinical data from the two health systems estimated from recent data. Based on our planned number of steps (7 with one uniformly applied usual care period across all hospital units), enrollment per study period, and a reasonable ICC of 0.01, the design effect is 2.72. Thus, we will need to obtain outcome data from the records of at least 2394 subjects overall (1197 per health system) to provide 80% power for our analysis of intervention effectiveness. We anticipate, however, that as many as 15,000 records will be available for analysis with respect to the documentation of ACP. Thus, our planned sample size for our primary records-based analysis on 15,000 records will therefore provide more than adequate power to test for differences in our primary outcome.

Data for Aim 1 is derived from the EHR and as is typical for trials that integrate new initiatives within the workflow of large institutions in a SW-CRT that does not involve consent. Indeed, we have been previously approved by multiple IRBs for such activities. Along with our exceedingly efficient NLP-assisted and human-confirmed software method for EHR data extraction, we can have a very large study sample with for this activity.

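### If the random-effects option for the primary analysis is fitted with a hospital-unit intercept only, unit-specific shifts between 2-month periods could push its false-positive rate above 5%

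*Combined protocol and SAP*

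**What the plan says.** Section 12.3 (Statistical Methods) promises methods that respect the correlation in the data and the influence of time, and states that "we will examine both the health system and hospital unit as clustering variables, with the hospital unit as the primary clustering variable". The primary-outcome paragraph then leaves two routes open for the logistic model. One is GEE with robust variance, clustering on hospital site and/or health system. The other is "or the inclusion of a random effects terms (in which case, the results will be interpreted as cluster-specific"). Secular trend is to be examined and incorporated. The structure of the random effects is not given, and neither a unit-by-period effect nor any decay of correlation over time is mentioned. Similar procedures are to be used for the other EHR outcomes.

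Section 12.2 (Sample Size Determination) uses one correlation value: "a reasonable ICC of 0.01, the design effect is 2.72". From this it concludes that "we will need to obtain outcome data from the records of at least 2394 subjects overall (1197 per health system"), while expecting up to 15,000. Section 4.1 gives 9,000 for the same aim. Section 5 sets out 14 randomized units, two per step, and eight periods of two months.

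**The concern.** A unit intercept makes two patients from the same unit equally correlated whether they were admitted in the same period or a year apart. If staffing, case mix or local documentation habits move one unit up or down between periods, patients in the same unit-period are more alike than that model allows. A secular trend common to all units does not absorb such shifts, and neither does a health-system term.

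This matters more here than in a small trial. With 80 to 134 patients per unit-period, patient-level noise in a unit-period proportion is small, so even modest unit-period shifts make up a sizeable part of the real error. The reported standard error would then be too small, the confidence interval too narrow, and a null intervention declared effective more often than the nominal 5%.

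**Working it through.** **The plan's own figures.** Two-group n for "35% in the intervention group compared to 25% in the usual care group", two-sided alpha 0.05:

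n = [1.96·√(2·0.30·0.70) + z·√(0.25·0.75 + 0.35·0.65)]² / 0.10²

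With z = 0.8416 (80% power) this gives 329 per group. With z = 1.2816 (90%) it gives 440. The stated 440 is therefore the 90% figure. That is conservative and does not bear on this point. Then 880 × 2.72 = 2,393.6, which reproduces 2,394. The standard cross-sectional stepped-wedge design effect with one ICC (7 steps, 1 baseline period) returns 2.72 at about 60 patients per cluster-period, a size the documents do not state.

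**Inputs for the check.** From the documents: 14 units, 8 periods, two units crossing per step, baseline 25% (variance 0.25 × 0.75 = 0.1875), ICC ρ = 0.01. Assuming equal cells, m = 15,000/112 ≈ 134, 9,000/112 ≈ 80 and 2,394/112 ≈ 21 per unit-period. Not in the documents, so assumed and varied: the cluster autocorrelation c (between-period over within-period correlation), and ρ = 0.03 as a higher ICC.

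**Model.** In units of the outcome variance, the true covariance of a unit's eight period proportions is

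V = ρc·J + [ρ(1 − c) + (1 − ρ)/m]·I

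where J is the all-ones matrix. The unit-intercept model fits W = τ²·J + (s²/m)·I, with τ² and s² at the values its likelihood converges to. D is each unit's design matrix (treatment plus eight period effects) and B = (ΣD′W⁻¹D)⁻¹. The reported variance is the treatment entry of B. The true variance is that entry of B(ΣD′W⁻¹VW⁻¹D)B. The false-positive rate is 2·[1 − Φ(1.96 × reported SE / true SE)].

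**Results, unit intercept only, z reference**

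| Records (per unit-period) | ICC | c = 1 | c = 0.9 | c = 0.8 | c = 0.5 |
|---|---|---|---|---|---|
| 15,000 (134) | 0.01 | 5.0% | 6.5% | 7.9% | 12.2% |
| 9,000 (80) | 0.01 | 5.0% | 5.8% | 6.7% | 9.1% |
| 2,394 (21) | 0.01 | 5.0% | 5.2% | 5.4% | 5.9% |
| 15,000 (134) | 0.03 | 5.0% | 9.8% | 14.4% | 25.4% |
| 9,000 (80) | 0.03 | 5.0% | 7.8% | 10.6% | 18.0% |

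Two worked cells at 15,000:
- ICC 0.01, c = 0.5: reported SE 1.180 points, true 1.494; 1.96 × 1.180/1.494 = 1.548, giving 12.2%.
- ICC 0.03, c = 0.8: reported 1.215, true 1.629; 1.96 × 1.215/1.629 = 1.462, giving 14.4%.

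A hand check shows why size matters. At ρ = 0.01 and c = 0.8 the unit-period variance is 0.01 × 0.2 = 0.002. Patient noise is 0.99/134 = 0.0074 at 15,000 records (the shift adds 27%) but 0.99/21.4 = 0.046 at 2,394 (it adds 4%).

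Simulated binary data (1,500 runs per setting, ICC 0.01) agree within Monte Carlo error: 4.8%, 7.1%, 9.1% and 11.6% for c = 1, 0.9, 0.8 and 0.5 at 15,000, and 6.1%, 6.9%, 7.3% and 10.0% at 9,000.

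**The GEE route.** In the same simulations, unit-clustered robust variance with a z reference rejected in about 9-11% of null trials whatever the autocorrelation, including 9.0% at c = 1 (15,000). That is few-cluster bias, a different mechanism.

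**With a unit-by-period intercept added** (134 per unit-period, ICC 0.01, c from 1 to 0.2, 2,500 runs each): 5.2-5.8% with z, and 5.0-5.4% with t on 112 − 14 − 8 = 90 degrees of freedom.

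**The case against.** The strongest reply is that the plan never says its random effects are a unit intercept only. It leaves the structure open and promises to account for time, and naming the unit as the primary clustering variable does not exclude a nested unit-by-period term. That stands: this is an omission that permits the weaker model, not a stated assumption. But a model built from the levels that are named would not contain the missing term.

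Other parts of the reply also stand:

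- No autocorrelation is given, and at 0.9-1 with ICC 0.01 the inflation is slight. A reader might take a single inflated rate as established; the documents do not support one.
- A reader might infer that the single ICC in Section 12.2 itself inflates the false-positive rate. It does not. A planning ICC bears on planned N and power.
- A reader might infer that robust GEE shares the defect. Unit-level robust variance does not rely on equal correlation across periods. Its problem here is having only 14 units.
- Section 12.2 puts effect size ahead of p-values and sets 10 points as the benchmark. In the 15,000-record, ICC 0.03, c = 0.8 case, a false positive needs an estimate of only 1.96 × 1.215 ≈ 2.4 points, while 10 points is 10/1.63 ≈ 6 true standard errors. A null effect would not plausibly be read as meeting the benchmark.
- The calculations are on the probability scale with equal cells, not the logistic model with unequal units. Section 7.1 ties the 15,000 to 23 units; spread that way, cells hold about 82 patients and the 9,000 rows are the better guide to cell size.

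**Conclusion.** The concern holds as a conditional one. One of the two permitted primary models, if fitted with only the clustering levels named, could be anti-conservative at the enrolment the plan expects. At the plan's own ICC the excess ranges from nothing to about 7 percentage points (15,000) or 4 (9,000) as autocorrelation falls from 1 to 0.5. It is larger at a higher ICC, and negligible at the 2,394-record minimum. These figures rest on assumed autocorrelations, equal cells, a linear-scale approximation and a z reference.

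The documents do not show that the plan has adopted a unit-intercept model, that the sample size is inadequate, or that the GEE route fails for this reason. Power to detect 25% versus 35% at ICC 0.01 stays above 99% at 9,000 or 15,000 records and is about 93% at 2,394, with the unit-period correlation allowed for. What is at stake is the validity of the nominal 5% level and the width of the interval. The model should be fixed in advance.

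**What to change.** In Section 12.3, primary-outcome paragraph:

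- Choose the primary model. If random effects, specify a unit random intercept plus a unit-by-period random intercept, 2-month periods as categorical fixed effects, and a small-sample reference such as t with between-cluster degrees of freedom (14 − 2 = 12).
- If GEE, cluster on hospital unit rather than site or health system (two sites cannot support a robust variance), and use a small-sample-corrected robust variance. Changing the working correlation alone would not cure the few-cluster bias.
- Report sensitivity of the result to the assumed between-period correlation.
- Apply the same structure to the secondary EHR outcomes.

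In Section 12.2, state the between-period correlation assumed, for transparency about N and power.

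The cost is wording and a slightly larger standard error: at 9,000 records and ICC 0.01, about 1.53 points at c = 1 against 1.62 (c = 0.8) and 1.71 (c = 0.5). The t reference on 12 degrees of freedom may be mildly conservative: a small simulation (250 runs per setting, so about ±2.7 points at a 5% rate) gave 1-4% false positives.
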